14.2.28 Data handling and programming rules

The following section should be used as guidance for development of the protocol, data handling procedures or programming requirements (e.g. on incomplete dates).

14.2.29 Study/project specific decisions

For each study (or project) various issues need to be addressed and specified in the protocol or RAP documentation. Any deviations from protocol must be discussed and defined at the latest in the RAP documentation.

The proposed primary analysis and potential sensitivity analyses should be discussed and agreed with the health authorities and documented in the protocol (or at the latest in the RAP documentation before database lock).

14.2.30 End of treatment phase completion

Patients **may** voluntarily withdraw from the study treatment or may be taken off the study treatment at the discretion of the investigator at any time. For patients who are lost to follow-up, the investigator or designee should show "due diligence" by documenting in the source

documents steps taken to contact the patient, e.g., dates of telephone calls, registered letters, etc.

The end of treatment visit and its associated assessments should occur within 7 days of the last study treatment.

Patients may discontinue study treatment for any of the following reasons:

- Adverse event(s)
- Lost to follow-up
- Physician decision
- Pregnancy
- Protocol deviation
- Technical problems
- Subject/guardian decision
- Death
- Progressive disease
- Study terminated by the sponsor
- Non-compliant with study treatment
- No longer requires treatment
- Treatment duration completed as per protocol (optional, to be used if only a fixed number of cycles is given)

14.2.31 End of post-treatment follow-up (study phase completion)

[figure not shown]
End of post-treatment follow-up visit will be completed after discontinuation of study treatment and post-treatment evaluations but prior to collecting survival follow-up.

Patients may provide study phase completion information for one of the following reasons:

- Adverse event
- Lost to follow-up
- Physician decision
- Pregnancy
- Protocol deviation
- Technical problems
- Subject/guardian decision
- Death
- New therapy for study indication
- Progressive disease
- Study terminated by the sponsor

14.2.32 Medical validation of programmed overall lesion response

As RECIST is very strict regarding measurement methods (i.e. any assessment with more or less sensitive method than the one used to assess the lesion at baseline is considered UNK)

and not available evaluations (i.e. if any target or non-target lesion was not evaluated the whole overall lesion response is UNK unless remaining lesions qualified for PD), these UNK assessments may be re-evaluated by clinicians at Novartis or external experts. In addition, data review reports will be available to identify assessments for which the investigators' or central reader's opinion does not match the programmed calculated response based on RECIST criteria. This may be queried for clarification. However, the investigator or central reader's response assessment will never be overruled.

If Novartis elect to invalidate an overall lesion response as evaluated by the investigator or central reader upon internal or external review of the data, the calculated overall lesion response at that specific assessment is to be kept in a dataset. This must be clearly documented in the RAP documentation and agreed before database lock. This dataset should be created and stored as part of the 'raw' data.

Any discontinuation due to 'Disease progression' without documentation of progression by RECIST criteria should be carefully reviewed. Only patients with documented deterioration of symptoms indicative of progression of disease should have this reason for discontinuation of treatment or study evaluation.

14.2.33 Programming rules

The following should be used for programming of efficacy results:

14.2.34 Calculation of 'time to event' variables

Time to event = end date - start date + 1 (in days)

When no post-baseline tumor assessments are available, the date of randomization/start of treatment will be used as end date (duration = 1 day) when time is to be censored at last tumor assessment, i.e. time to event variables can never be negative.

14.2.35 Incomplete assessment dates

[figure not shown]
All investigation dates (e.g. X-ray, CT scan) must be completed with day, month and year.

If one or more investigation dates are incomplete but other investigation dates are available, this/these incomplete date(s) are not considered for calculation of the assessment date (and assessment date is calculated as outlined in [Section 14.2.25](#)). If all measurement dates have no day recorded, the 1st of the month is used.

If the month is not completed, for any of the investigations, the respective assessment will be considered to be at the date which is exactly between previous and following assessment. If a previous and following assessment is not available, this assessment will not be used for any calculation.

14.2.36 Incomplete dates for last known date patient alive or death

All dates must be completed with day, month and year. If the day is missing, the 15th of the month will be used for incomplete death dates or dates of last contact.

[figure not shown]
[figure not shown]

14.2.37 Non-target lesion response

If no non-target lesions are identified at baseline (and therefore not followed throughout the study), the non-target lesion response at each assessment will be considered ‘not applicable (NA)’.

14.2.38 Study/project specific programming

The standard analysis programs need to be adapted for each study/project.

14.3 Appendix 3: Response assessment in neuro-oncology (RANO) criteria for high-grade gliomas

Antitumor response will be primarily evaluated by the Response Assessment in Neuro-Oncology (RANO) working group ([Wen et al 2010](#)) criteria in this study. The RANO Criteria updates its established predecessor, the modified Macdonald Criteria ([Macdonald et al 1990](#)), by adding assessment of non-enhancing lesions.

Patients will undergo Contrast MRI assessments for response evaluation starting at Week 8 and every 8 weeks thereafter to evaluate brain lesions, as outlined in the Visit schedule [Table 7-1](#) and [Table 7-2](#).

The following components will be taken into account when assessing a patient's overall response at an individual evaluation.

- Tumor evaluation eCRF page for measureable enhancing lesions (T1-Gd+)
- Tumor evaluation eCRF page for non-measurable enhancing lesions (T1-Gd+)
- Tumor evaluation eCRF page for non-enhancing lesions (T2/FLAIR)
- Tumor evaluation eCRF page for new lesion
- Concomitant medication eCRF page for steroid usage
- Clinical status eCRF page for KPS and other clinical evaluation finding
- Overall response eCRF page for response category (CR/PR/PD/SD/NA)

14.3.1 Antitumor effect - definitions

Evaluable for toxicity

All participants who receive at least one dose of study treatment will be evaluable for toxicity from the time of their first treatment.

Evaluable for objective response

Only those participants who have measurable disease present at baseline (cycle 1, day 1 scan) and have received at least one dose of therapy will be considered evaluable for response. These participants will have their response classified according to the definitions stated below. (Note: Participants who exhibit objective disease progression or die prior to the end of cycle 1 will also be considered evaluable.)

Measurable disease

Bidimensionally, contrast-enhancing, measurable lesions with clearly defined margins by CT or MRI scan, with a minimal diameter of 10mm, and visible on 2 axial slices which are at least 5 mm apart with 0 mm skip. Measurement of tumor around a cyst or surgical cavity, if necessary, requires a minimum thickness of 3 mm. If there are multiple measurable lesions, the investigator must choose a minimum of two and a maximum of five of the largest lesions to be followed before a participant is entered on study. The remaining lesions will be considered non-measurable for the purpose of objective response determination. Unless

progression is observed, objective response can only be determined when all measurable and non-measurable lesions are assessed.

Non-measurable evaluable disease

Unidimensionally measurable lesions, masses with margins not clearly defined, lesions with maximal diameter < 10mm.

14.3.2 Response/progression categories

Complete response (CR)

All of the following criteria must be met:

- a. Complete disappearance of all enhancing measurable and non-measurable disease sustained for at least 4 weeks. In the absence of a confirming scan 4 weeks later, this scan will be considered only stable disease.
- b. No new lesions.
- c. All measurable and non-measurable lesions must be assessed using the same techniques as baseline.
- d. Participants must be on no steroids or on physiologic replacement doses only.
- e. Stable or improved non-enhancing (T2/FLAIR) lesions
- f. Stable or improved clinically, for clinical signs and symptoms present at baseline and recorded to be disease related

[figure not shown]
Participants with non-measurable disease cannot have a complete response. The best response possible is stable disease.

Partial response (PR)

All of the following criteria must be met:

- a. Greater than or equal to 50% decrease compared to baseline in the sum of products of perpendicular diameters of all measurable enhancing lesions sustained for at least 4 weeks. In the absence of a confirming scan 4 weeks later, this scan will be considered only stable disease.
- b. No progression of non-measurable disease.
- c. No new lesions.
- d. All measurable and non-measurable lesions must be assessed using the same techniques as baseline.
- e. The steroid dose at the time of the scan evaluation should be no greater than the dose at time of baseline scan.
- f. Stable or improved non-enhancing (T2/FLAIR) lesions on same or lower dose of corticosteroids compared to baseline scan.
- g. Stable or improved, for clinical signs and symptoms present at baseline and recorded to be disease related clinically.

Participants with non-measurable disease cannot have a partial response. The best response possible is stable disease.

Progressive disease (PD)

The following criterion must be met:

- a. 25% increase in sum of the products of perpendicular diameters of enhancing lesions (over best response or baseline if no decrease) on stable or increasing doses of corticosteroids **and/or one or more of the of the following:**
- b. Significant increase in T2/FLAIR non-enhancing lesion on stable or increasing doses of corticosteroids compared to baseline scan or best response following initiation of therapy, not due to co-morbid events (radiation therapy, demyelination, ischemic injury, infection, seizures, post-operative changes, or other treatment effects).
- c. Any new lesion
- d. Clear clinical deterioration not attributable to other causes apart from the tumor (e.g. seizures, medication side effects, complications of therapy, cerebrovascular events, infection, etc.). The definition of clinical deterioration is left to the discretion of the investigator but it is recommended that a decline in the Karnofsky Performance Score (KPS) from 100 or 90 to 70 or less, a decline in KPS of at least 20 from 80 or less, or a decline in KPS from any baseline to 50 or less, for at least 7 days, be considered neurologic deterioration, unless attributable to co-morbid events or changes in corticosteroid dose.
- e. Failure to return for evaluation due to death or deteriorating condition.
- f. Clear progression of non-measurable disease

Stable disease (SD)

All of the following criteria must be met:

- a. Does not qualify for CR, PR, or progression.
- b. All measurable and non-measurable sites must be assessed using the same techniques as baseline.
- c. Stable non-enhancing (T2/FLAIR) lesions on same or lower dose of corticosteroids compared to baseline scan. In the event that the corticosteroid dose has been increased, the last scan considered to show stable disease will be the scan obtained when the corticosteroid dose was equivalent to the baseline dose.
- d. Stable clinically.

Unknown response status

Progressive disease has not been documented and one or more measurable or non-measurable lesions have not been assessed.

These RANO Response Criteria are also summarized in [Table 14-10](#):

[figure not shown]

Table 14-10 Summary of the RANO response criteria

	CR	PR	SD	PD#
T1-Gd +	None	≥50% decrease	<50% decrease but <25% increase	≥25% increase*
T2/FLAIR	Stable or decrease	Stable or decrease	Stable or decrease	Increase*
New Lesion	None	None	None	Present**
Corticosteroids	None	Stable or decrease	Stable or decrease	NA**
Clinical Status	Stable or improve	Stable or improve	Stable or improve	Deterioration*
Requirement for Response	All	All	All	Any*

CR=complete response; PR=partial response; SD=stable disease; PD=progressive disease
*: Progression when this criterion is met **: Increase in corticosteroids alone will not be taken into account in determining progression in the absence of persistent clinical deterioration

14.3.3 Methods for evaluation of measurable disease

All measurements should be taken and recorded in metric notation, using a ruler, calipers, or digital measurement tool. All baseline evaluations should be performed as closely as possible to the beginning of treatment and never more than 14 days before the beginning of the treatment.

The same method of assessment and the same technique should be used to characterize each identified and reported lesion at baseline and during follow-up.

14.3.4 Evaluation of best response

The best overall response is the best response recorded from the start of the treatment until disease progression (taking as reference for progressive disease the smallest measurements recorded since the treatment started). If a response recorded at one scheduled MRI does not persist at the next regular scheduled MRI, the response will still be recorded based on the prior scan, but will be designated as a non-sustained response. If the response is sustained, i.e. still present on the subsequent MRI, it will be recorded as a sustained response, lasting until the time of tumor progression. Participants without measurable disease may only achieve SD or PD as their best “response.”

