6.4.1 Permitted concomitant therapy

6.4.1.1 Corticosteroids

Chronic dosing of corticosteroids such as dexamethasone and prednisone is known to induce CYP3A enzymes, thereby increasing the risk of reducing ceritinib drug exposure to sub-therapeutic levels.

If possible, systemic corticosteroid treatment should not be given during the study, except for:

- Topical applications (e.g. rash), inhaled sprays (e.g. obstructive airways diseases), eye drops or local injections (e.g. intra-articular);
- If clinically indicated, corticosteroid therapy such as dexamethasone or prednisone may be used to control CNS tumor associated symptoms. All efforts will be made to minimize the dose of corticosteroids to what is strictly needed and to decrease dose as soon as possible. If dose needs to be increased to control CNS tumor associated symptoms, all efforts will be made to stabilize (or decrease) the dose for at least 5 days before the first dose of study treatment. **Note:** Dose of steroids must be stable for 5 days before the baseline brain MRI. Every effort should be made to maintain a stable (or decreasing) dose of steroids in subsequent brain MRIs.

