## 2.8 Analysis of secondary variables

### 2.8.1 Efficacy

Table 2-1 summarizes all tumor related endpoints and the population for analysis. The definitions and details on the derivation of the secondary endpoints are given in the following sections. Confirmation of response is required for all response endpoints, as per RECIST 1.1 and RANO. Further details and rules needed for programmatic implementation of RECIST 1.1 guidelines and RANO guidelines are provided in Section 4.6.1 and Section 4.6.2 respectively.

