##### Overall Lesion Response Collected on RANO eCRF page

Intracranial endpoints by RANO will be derived based on the collected overall lesion response on eCRF page “RANO Overall Lesion Response” (ZR domain, ZRCAT = “RESPONSE ASSESSMENT IN NEURO-ONCOLOGY”, and ZRSCAT = “OVERALL LESION RESPONSE”). The derivation of intracranial endpoints (OIRR, IDCR, DOIR, TTIR and TTP in the brain) by RANO is the same as by RECIST 1.1.

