**Table 4-3 Summary of the RANO response criteria**

	CR	PR	SD	PD
T1-Gd+ target lesions	None	≥50% decrease from baseline	<50% decrease from baseline but <25% increase from nadir	≥25% increase from nadir*
T1-Gd+ non-target lesions	Stable or improved	Stable or improved	Stable or improved	Increase*
T2/FLAIR	Stable or improved	Stable or improved	Stable or improved	Increase*
New Lesion	None	None	None	Present*
Corticosteroids	None	Stable or decrease	Stable or decrease	NA**
Clinical Status	Stable or improve	Stable or improve	Stable or improve	Deterioration*
Requirement for Response	All	All	All	Any*
CR=complete response; PR=partial response; SD=stable disease; PD=progressive disease *: Progression when this criterion is met **: Increase in corticosteroids alone will not be taken into account in determining progression in the absence of persistent clinical deterioration				

Two fields in the Modified RANO Assessment page will not be used for any data analysis in the study: “New enhancement outside radiation field?”, “Tumor present in histopathology”.

As in RECIST 1.1, PD should only be assigned if it is demonstrated by an objective assessment method as per RANO. Discontinuation due to disease progression or death due to progressive disease, without supporting objective evidence, will not be considered as PD.

As in RECIST 1.1, the same method of assessment and the same technique should be used to characterize each identified and reported lesion at baseline and during follow-up. The details of change in imaging modality are described in [Section 4.6.1](#).

The same principle will be followed for determining missing adequate tumor assessments, as described in [section 4.6.1](#).

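### Appendix 3 states two RANO rules inconsistently: growth during a steroid taper can be coded as progression or not, and visit-level coding of an unconfirmed response is left open (exploratory endpoints only)

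*Protocol*

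**What the plan says.** **Progression.** Protocol 14.3.2 makes a 25% increase in enhancing lesions PD if steroids are stable or rising. Its non-enhancing criterion begins "Significant increase in T2/FLAIR non-enhancing lesion on stable or increasing doses of corticosteroids compared to baseline scan or best response" and goes on to exclude radiation and other co-morbid or treatment effects. Table 14-10, presented as a summary of these criteria, gives the 25% increase and the T2/FLAIR increase without conditions. It marks the steroid entry as not applicable and explains its asterisk as "Progression when this criterion is met". Its other footnote deals only with a rise in steroid dose. SAP Table 4-3 repeats this version, with the enhancing entry "≥25% increase from nadir". In both tables SD requires enhancing growth below 25%.

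**Confirmation.** For CR and for PR, 14.3.2 says "In the absence of a confirming scan 4 weeks later, this scan will be considered only stable disease". For a response that has gone by the next scheduled MRI, 14.3.4 says "the response will still be recorded based on the prior scan, but will be designated as a non-sustained response". SAP 2.8.1 says "Confirmation of response is required for all response endpoints, as per RECIST 1.1 and RANO", and SAP 2.7.1 asks for two qualifying readings four or more weeks apart before progression. SAP 4.6.2 carries the RECIST derivation over to RANO, working from the reported visit category: "Intracranial endpoints by RANO will be derived based on the collected overall lesion response on eCRF page".

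**The concern.** The RANO endpoints rest on the category that the investigator or the BIRC reports at each visit. If Appendix 3 allows two categories for one MRI, two readers can follow the protocol correctly and disagree.

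The progression conflict is the live one, because the SAP repeats the unconditional version and nowhere resolves it. The situation is foreseeable: Protocol 6.4.1.1 asks sites to keep steroids to the minimum and "to decrease dose as soon as possible", and accepts a falling dose at later brain MRIs.

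The confirmation conflict is mostly closed by the SAP. What remains is the input. The 14.3.2 definitions of CR and PR already contain a four-week persistence requirement, and the SAP then applies confirmation to the reported categories. Nothing says how the first responding MRI is to be entered before its confirming scan exists. At stake is whether RANO results can be compared between readers, and with the modified-RECIST results.

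**Working it through.** The documents give no sample size, precision or event figure for a RANO endpoint, so there is no stated figure to reproduce. The check sets the rules side by side and applies each to hypothetical MRI series.

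**1. The PD rules compared**

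| Element | 14.3.2 text | Table 14-10 and SAP Table 4-3 |
|---|---|---|
| Enhancing growth | 25%, steroids stable or rising | 25% alone |
| T2/FLAIR | Significant, steroids stable or rising, not from radiation or another co-morbid cause | Any increase |
| Steroids | Part of the criterion | Not applicable; note covers a dose rise only |
| SD | Not CR, PR or PD, with T2/FLAIR and clinical status stable | Enhancing growth under 25% |

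Enhancing growth of 25% on a falling dose, otherwise stable, is SD by the text. By the tables it meets PD and cannot be SD. For T2/FLAIR, an increase excused by the text is not PD, but the text's SD also asks for stable non-enhancing lesions, so it has no clear category there. The radiation exclusion belongs to T2/FLAIR only. Enhancing growth has none in either place.

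**2. Effect on the endpoints**

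Inputs: sums of products at baseline and weeks 8, 16 and 24 (assumed). The steroid dose is lower at the visit with growth; there is no new lesion, and T2/FLAIR and clinical status are stable. Change from nadir = 100 × (current sum / smallest earlier sum − 1).

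- *DOIR.* 1000 / 450 / 450 / 600. Week 8: 100 × (450/1000 − 1) = −55%, confirmed at week 16. Week 24: 100 × (600/450 − 1) = +33.3%. Tables: PD at week 24, so DOIR ends. Text: no PD, so DOIR continues.
- *IDCR, growth at the first evaluation.* 1000 / 1300. Week 8: 100 × (1300/1000 − 1) = +30%. Tables: PD within 17 weeks, not controlled. Text: SD after more than 7 weeks, controlled (SAP 2.7.1).
- *IDCR, later growth.* 1000 / 1000 / 1300. The +30% comes at week 16. SD at week 8 already fixes best response as SD under both rules, so overall IDCR does not change. SAP Table 2-1 lists no week-8 or week-16 IDCR by RANO.
- *OIRR and TTIR.* 1000 / 1300 / 450 / 450. Tables: PD at week 8 precedes any response, so the patient is a non-responder. Text: SD, then PR at weeks 16 and 24, so a confirmed responder with TTIR at week 16. MRIs would continue, because Protocol 4.1.2.1 stops them at RECIST progression, not at a RANO call.

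**3. Confirmation**

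- *Unconfirmed response.* 1000 / 450 / 550. Week 8: −55%. Week 16: 100 × (550/1000 − 1) = −45% from baseline and 100 × (550/450 − 1) = +22.2% from nadir, not PD by either version. 14.3.2 gives SD; 14.3.4 gives a non-sustained response. The SAP finds one qualifying reading, so best response is SD. IDCR counts the patient as controlled under all three.
- *First responding MRI entered as SD and not revised.* 1000 / 450 / 450 / 600. With week 8 entered as PR, weeks 8 and 16 confirm the response and TTIR is week 8. With week 8 left as SD, only week 16 qualifies and the patient is a non-responder. Had week 24 been 450 again, weeks 16 and 24 would confirm, with TTIR 16 − 8 = 8 weeks later and DOIR 8 weeks shorter. Three responding MRIs are then needed where the SAP intends two.

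**The case against.** On confirmation the plan has a strong answer. SAP 2.8.1, 2.7.1 and 4.6.2 together require two readings and apply the RECIST derivation to RANO, so 14.3.4 cannot create a responder in the analysis. This stands. The three-MRI outcome also needs a site to enter the first responding scan as SD and never correct it, and no passage says that sites do so. The 14.3.2 wording can be read as a retrospective downgrade, both tables define PR with no persistence clause, and Protocol 7.2.1.2 allows off-schedule confirmation scans. The second point is therefore residual: a coding instruction is missing, and no error has been shown.

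On progression, Table 14-10 can be defended as shorthand for the text. The mark on its PD column heading has no matching note in the available text, so a note may have been lost. SAP Table 4-3 does not generate the endpoints, which use the reported category, and SAP 4.6.2 refers back to Appendix 3. This narrows the conflict to variation between readers but does not remove it. The tables do more than leave conditions out: they say that any one criterion suffices, and their SD entry rules out growth of 25%. SAP Table 4-3 has no marked heading and repeats the same rule. SAP 4.6.2 also calculates a RANO response from components beside that table, so calculated and reported categories can differ.

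**Conclusion.** Both inconsistencies are in the current text. The progression conflict is live and can act on DOIR, on IDCR at the first evaluation, and on OIRR and TTIR when the disputed growth precedes confirmation. The confirmation conflict is settled for analysis and survives only as a possible coding difference. No reliable size can be given: the documents do not say how often growth occurs on a taper, or how sites enter a first responding MRI. The endpoints are exploratory (Protocol 10.6) in an estimation study without hypothesis tests (SAP 2.7.2).

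Three stronger conclusions are tempting and not supported.

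- A reader might infer that every RANO endpoint is open on both counts. Response versus SD cannot move IDCR, which counts both, and later disputed growth generally leaves overall IDCR unchanged.
- A reader might infer bias against the irradiated Arms 1 and 3. The radiation exclusion covers T2/FLAIR only, no document shows more such change in those arms, and entry criterion 13 accepts an enlarging SRS-treated lesion only if the growth is tumoral.
- A reader might infer a reported OIRR of 50% that falls once confirmation is applied, or a stated shift in IDCR. The 50% of 70 patients in Protocol 10.9 is an illustration for confirmed modified-RECIST responses. An unconfirmed rate would not be reported under the SAP, and any IDCR shift would be pure assumption.

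**What to change.** 1. State one PD rule across Protocol 14.3.2, Table 14-10 and SAP Table 4-3. Carry the text's steroid condition into the T1-Gd+ and T2/FLAIR PD cells, and add to the T2/FLAIR cell that the increase must be significant and not explained by radiation or another co-morbid cause.
2. Adjust the SD cells, and the non-enhancing item of SD in 14.3.2, so that growth not meeting PD has a category. Changing the PD cells alone would leave it neither SD nor PD in the tables.
3. Delete the sentence in 14.3.4 that keeps an unconfirmed response, or align it with the SAP.
4. State in SAP 4.6.2 that visit-level CR and PR are coded on the scan, steroid and clinical thresholds, that confirmation is applied once in the best-response derivation, and that TTIR and DOIR are dated from the first scan of the confirmed pair.

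The cost is wording in the appendix and the SAP, plus a check of the RANO eCRF and BIRC entries for first responding MRIs and for PD recorded on a falling steroid dose. No new data or patients are needed.
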